#### **Part 2: MRD in Healthy Subjects**

Part 2 will consist of 3 cohorts of subjects, sequential multiple-dose panels, with a double blind design. Three dose cohorts, Cohorts 6, 7, and 8, are considered adequate to explore the pharmacologically active exposure range. Each cohort will be comprised of 8 subjects, where 6 subjects will be randomized to receive TAK-418 and 2 subjects will be assigned to receive matched placebo. The trial population for Part 2 will be comprised of approximately 24 healthy subjects. Part 2 may commence after completion of SRD Cohort 3A in Part 1, in which the starting dose will not exceed the dose tested in Cohort 3A from Part 1.

It is planned that subjects will receive once-daily (QD) dosing of TAK-418 or matching placebo for 7 days to achieve steady-state. The mean terminal disposition phase half-life ( $t_{1/2z}$ ) of TAK-418 from Part 1 will inform the duration of dosing required in Part 2 to achieve steady-state.

Two wearable digital devices, an actigraphy device and an ECG device, will be applied from Day -1 in subjects who consent to be in this additional exploratory part of the trial. Both devices will be used continuously through the dosing procedures, the postdosing period while subjects are in the unit, and for approximately 6 days after the subjects' discharge from the unit. Subjects will return the devices to the unit at the follow-up visit.

The trial schedule is detailed in Table 6.c.

[Table 6.c Part 2: Trial Schedule]

#### **Rationale for Change:**

Change in study design to exclude MRD part of the study, include male subjects with normal and to provide additional clarification.

[figure not shown]
The following sections also contain this change:

- Title Page
- Section 1.0 STUDY SUMMARY
- Section 2.0 Trial Schematic
- Section 3.0 Schedule of Trial Procedures
- Section 5.1.1 Primary Objective
- Section 5.1.2 Secondary Objective
- Section 5.1.3 Exploratory Objectives
- Section 6.2 Dose Escalation
- Section 6.3 Justification for Trial Design, Dose, and Endpoints
- Section 6.3.3.1 Safety and PK
- Section 6.3.3.2 Exploratory Endpoints
- Section 6.4 Trial Design/Dosing/Procedures Modifications Permitted Within Protocol Parameters
- Section 6.5.3 Definition of Trial Completion
- Section 9.2.7 Trial Drug Administration
- Section 9.3 Biomarker, PK, PD, and PGx, Samples
- Section 9.3.1 PK Measurements
- Section 9.3.5 Confinement
- Section 11.1.3 PK Analysis
- Section 11.1.6 Safety Analysis
- Section 11.3 Determination of Sample Size

Change 2: Added objectives relating to CCI

The primary change occurs in 5.1 Objectives

Added text: 5.1.3 Exploratory Objectives

## **Rationale for Change:**

#### CCI

The following sections also contain this change:

- Section 1.0 STUDY SUMMARY
- Section 4.3 Benefit/Risk Profile
- Table 6.b Trial Schedule
- Section 6.2 Dose Escalation
- Section 6.3.2 Dose
- Section 9.3 Biomarker, PK, PD, and PGx, Samples
- Section 9.3.2.3 CCI
- Section 9.3.3.2 Biological Sample Retention and Destruction
- Section 10.2.9.1 Collection Period

**Change 3:** Added inclusion and exclusion criteria based on in male subjects.

This primary change occurs in 7.1 Inclusion Criteria and 7.2 Exclusion Criteria

Added text 7.1 Inclusion Criteria

- 8. Male subjects must have CCI
- 7.2 Exclusion Criteria
- 10. Male subjects who have serum clinically abnormal.

## **Rationale for Change:**

To ensure that male subjects with normal function are enrolled.

The following sections also contain this change:

- Section 1.0 STUDY SUMMARY
- Section 3.0 Schedule of Trial Procedures
- Table 6.b Trial Schedule
- Section 9.2.11.2 Diagnostic Screening

**Change 4:** Added biomarkers.

This primary change occurs in Section 5.1.3 Exploratory Objectives

Added text:

- To collect plasma samples for possible exploratory biomarker analysis including but not limited to brain-derived neurotrophic factor (BDNF).
- CC

## **Rationale for Change:**

CCI

The following sections also contains this change:

- Section 5.2.3 Exploratory Endpoints
- Section 6.3.3.3 Biomarkers
- Section 9.3.2.2 Plasma Samples for Circulating Biomarkers
- Section 10.2.9.6 Exploratory Biomarkers and Data From Wearable Devices
- Section 11.1.5 Biomarker Analysis

Change 5: Added preliminary data from 13-week toxicology study.

This primary change occurs in Section 4.3 Benefit/Risk Profile

## **Rationale for Change:**

To provide observed color toxicity in nonclinical study and management of potential risk.

The following sections also contains this change.

- Section 1.0 STUDY SUMMARY
- Section 6.1 Trial Design
- Section 6.2 Dose Escalation

Amendment 01 to A Randomized, Double-Blind, Placebo-Controlled, Ascending Oral Single- and Multiple-Dose Trial to Evaluate the Safety, Tolerability, and Pharmacokinetics of TAK-418 in Healthy Subjects

3.0 LIST OF ABBREVIATIONS

AE adverse event
ANOVA analysis of variance

AUC area under the concentration-time curve

AUC₂₄ area under the serum concentration-time curve from time 0 to 24 hours

 AUC_{∞} area under the concentration-time curve from time 0 to infinity, calculated using the

observed value of the last quantifiable concentration

AUC_{last} area under the concentration-time curve from time 0 to time of the last quantifiable

concentration

BDNF brain-derived neurotrophic factor
BL-VAS Bond-Lader Visual Analogue Scale

BMI body mass index
CI confidence interval

C_{max} maximum observed concentration
 CPAP Clinical Pharmacology Analysis Plan
 C-SSRS Columbia Suicide Severity Rating Scale

%CV coefficient of variation
DBP diastolic blood pressure
ECG Electrocardiogram

eCRF electronic case report form

F free base

FAD flavin adenine dinucleotide

F-FAD formyl-flavin adenine dinucleotide

FIH first-in-human

hCG human chorionic gonadotropin
HIV human immunodeficiency virus

HR heart rate

MAV Markedly abnormal values

MedDRA Medical Dictionary for Regulatory Activities

mRNA messenger RNA miRNA micro RNA

NOAEL no-observed-adverse-effect level PBMC peripheral blood mononuclear cells

PD pharmacodynamic(s)
PGx pharmacogenomics
PK pharmacokinetic(s)
PT preferred term

PTE Pretreatment adverse event

QTcF QT interval with Fridericia correction method

RBC	red blood cell
SAE	serious adverse event
SAP	statistical analysis plan
SBP	systolic blood pressure
SD	Standard deviation
SOC	system organ class
SRD	single rising dose

 $\begin{array}{ll} t_{1/2z} & terminal \ disposition \ phase \ half-life \\ TEAE & treatment-emergent \ adverse \ event \\ t_{max} & time \ of \ first \ occurrence \ of \ C_{max} \end{array}$

ULN upper limit of normal WBC white blood cell

4.0 OBJECTIVES

4.1 Primary Objectives

The primary objective of this trial is to evaluate the safety and tolerability of TAK-418 following single oral doses in healthy subjects.

4.2 Secondary Objectives

The secondary objective of this trial is to evaluate the PK of TAK-418 free base (F) following a single oral dose (under fasted and fed states) in healthy subjects.

4.3 Exploratory Objectives

Exploratory objectives of the trial include:

4.4 Study Design

The study is a first-in-human (FIH), randomized, double-blind, placebo-controlled trial to evaluate the safety, tolerability, and PK of TAK-418 in healthy adult subjects aged from 18 to 55 years, inclusive. The study will also explore the PD of TAK-418 and its effects on selected biomarkers following single oral doses in healthy adult subjects.

This study will involve 40 subjects, equally divided among 5 sequential cohorts of 8 subjects each (with a minimum of 4 male subjects), as shown in Table 4.a. In each cohort, 6 subjects will

receive TAK-418 and 2 will receive matching placebo. To ensure adequate safety and tolerability, sentinel dosing will be used for Cohort 1 with only 2 subjects dosed on Day 1 (1 receiving TAK-418 and 1 receiving placebo). The remaining 6 subjects will be dosed in 2 groups of 3 subjects each after a review of 72-hour postdose safety and tolerability data of the previous group. A staggered dosing regimen will be used for Cohorts 2 to 5. Each cohort will be divided by 2 groups (3 active: 1 placebo), and the second group will be dosed 48 hours after the first group, following assessment of safety and tolerability data.

Additional cohorts may be studied if deemed necessary to fully characterize the pharmacologically active exposure range.

Table 4.a Schematic Doses for Cohorts 1 through 5

Dose 5 mg	Dose 15 mg	Dose 30 mg	Dose 40 mg	Dose 60 mg		
Cohort 1	Cohort 2	Cohort 3A and 3B	Cohort 4	Cohort 5		
(n=8; 6 active: 2 placebo)						

TAK-418 and placebo will be administered orally in capsule formulation and will be prepared and dispensed in a blinded fashion by an unblinded pharmacist or qualified trial site personnel. Doses planned to be administered range from 5 to 180 mg, but the actual doses administered after the first dose will be based on emerging safety and tolerability data from the previous doses. If needed, a dose higher than 180 mg but less than 300 mg may be evaluated providing its predicted exposure does not exceed the following exposure levels. The highest dose administered will have a predicted mean area under the plasma concentration-time curve (AUC) that does not exceed the monkey AUC at the no-observed-adverse-effect level (NOAEL; males) from the 13-week toxicology study or mean maximum observed concentration (Cmax) that does not exceed one-tenth of the monkey Cmax from the 4-week toxicology study.

Subjects in Cohort 3 will receive 2 doses (under fasted state [Cohort 3A] and fed state [Cohort 3B]), with at least 7 days washout between dose administrations. Subjects enrolled in Cohort 3A will return to the site to complete Cohort 3B and will be administered TAK-418/placebo under fed condition with a high fat/high calorie breakfast, which must be consumed within 30 minutes and the dose given within 5 minutes after the end of the meal. All assessments from Day -1 to Day 4 in Cohort 3B will be same as in Cohort 3A; however, there will be no follow-up for after Cohort 3A and the Day 14 follow-up assessment for Cohort 3B. For male subjects, days will be adjusted based on dosing in Cohort 3B.

The trial schedule is detailed in Table 4.b.

Table 4.b Trial Schedule

Screening	Pretreatment	Treat		
Period	(a)	Dose Administration (b)	Postdose Procedures (b)	Posttrial (c)
Days -28 to -2	Day -1	Day 1	Days 1 to 4	Day 14 (±2) (c)
				Days 91, 93, 182, and 184 (±7)

(a) CC

(b) Subjects will remain in the phase 1 unit for a minimum of 48 hours following the dose of trial drug and may be released after 48 hours and complete the 72 hour and later procedures at an outpatient visit. Subjects may be kept in the clinic for longer time at PI's discretion.

(c) CCI

5.0 ANALYSIS ENDPOINTS

5.1 Primary Endpoint

The primary endpoint of the study is a composite of safety variables and dose-limiting effects of TAK-418 that will be evaluated after dosing on Day 1 by the number and percentage of subjects who:

- Experience at least 1 treatment-emergent adverse event (TEAE).
- Discontinue because of an adverse event (AE).
- Meet the markedly abnormal criteria for neurological assessment measurements at least once postdose.
- Meet the markedly abnormal criteria for safety laboratory tests at least once postdose.
- Meet the markedly abnormal criteria for vital sign measurements at least once postdose.
- Meet the markedly abnormal criteria for safety 12-lead ECG parameters at least once postdose.

5.2 Secondary Endpoints

The secondary endpoints include:

Evaluation of the following PK parameters in healthy subjects after dosing on Day 1:

- Area under the concentration-time curve from time 0 to time of the last quantifiable concentration (AUC_{last}).
- Area under the concentration-time curve from time 0 to infinity (AUC $_{\infty}$).
- Maximum observed concentration (C_{max}).
- Time of first occurrence of $C_{max}(t_{max})$.

5.3 Exploratory Endpoints

Exploratory endpoints will be assessed through the following parameters in healthy subjects after dosing on Day 1:

6.0 DETERMINATION OF SAMPLE SIZE

The sample size of 8 subjects per cohort (6 active: 2 placebo) chosen is based upon precedents from other FIH trials rather than a formal assessment of statistical power.

Subjects who drop out for nonsafety reasons may be replaced on a case-by-case basis at the discretion of the sponsor in consultation with the investigator. Subjects who replace dropouts will be allocated to the same dose as the subject they replace. Subjects who drop out for safety reasons will not be replaced.

7.0 METHODS OF ANALYSIS AND PRESENTATION

7.1 General Principles

Continuous data will be summarized using the following descriptive statistics: number of subjects (N), mean, standard deviation (SD), median, minimum, and maximum, where appropriate. Where indicated, the coefficient of variation (%CV) and geometric mean will also be included in the summary of continuous data. Categorical data will be summarized using the number and percentage of subjects (N[%]) for each category, where applicable. Missing values will be categorized separately where deemed appropriate and necessary.

Baseline values are defined as the last observed values before the first dose of study drug, unless otherwise stated; baseline values for Cohort 3 are defined as the last observed values before the first dose of study drug in each period.

In general, the presentation of decimal points will follow the following rules as appropriate: minimum and maximum values will be presented using the same number of decimal places as the recorded data. Arithmetic means, geometric means, and medians will be presented to 1 more decimal place than the recorded data, and SDs will be presented to 2 more decimal places than the recorded data. The confidence interval (CI) for a parameter estimate will be presented using the same number of decimal places as the parameter estimate. Percentage will be presented to 1 decimal place (eg, 80.1%). All p-values will be rounded to 3 decimal places prior to assessment of statistical significance.

All study-related raw data for enrolled subjects, including derived data, will be presented in data listings. In addition, the actual day relative to the first dose will be presented, where applicable.

As applicable, summaries for the study will be presented by pooled placebo, each TAK-418 dose level, TAK-418 overall and overall total. Data from the food effect cohort (Cohort 3) will be summarized separately by placebo fed, placebo fasted, TAK-418 fed, and TAK-418 fasted.

All statistical analyses will be performed using the SAS System® Version 9.4 or higher.

7.1.1 Study Definitions

There are no study-specific definitions.

7.1.2 Definition of Study Days

Study Day 1 is defined as the date of the first dose of study drug, as recorded on the electronic case report form (eCRF) dosing page. Other study days are defined relative to Study Day 1, with Day 1 being Study Day 1 and Day -1 being the day prior to Study Day 1. Study days prior to the first dose of study drug will be calculated as: {date of assessment/event - date of first dose of study drug}. Study days on or after the first dose of study drug will be calculated as: {date of assessment/event - date of first dose of study drug + 1}.

7.1.3 Definition of Study Visit Windows

There will be no visit windowing.

7.1.4 Conventions for Missing Adverse Event Dates

There will be no imputation of incomplete or missing adverse event dates.

7.1.5 Conventions for Missing Concomitant Medication Dates

There will be no imputation of incomplete or missing concomitant medication dates.

7.1.6 Conventions for Missing Data

There will be no imputation of incomplete or missing data.

Plasma or urine concentrations that are below the limit of quantification (< BLQ) will be treated as zero in the summarization of concentration values and derivation of PK parameters.

7.2 Analysis Sets

The following analysis sets will be used for analysis and presentation of the study data:

- Safety Set: The safety set will consist of all subjects who receive at least 1 dose of trial drug.
 Subjects in this analysis set will be used for demographic, baseline characteristics, and safety summaries.
- Pharmacokinetic (PK) Set: The PK set will consist of all subjects who receive at least 1 dose of trial drug and have at least 1 measurable plasma concentration or amount of drug in the urine for TAK-418. All subjects with valid PK parameter estimates will be included in the summaries and analyses for that parameter.

• CCI

If any subject is found to be noncompliant with the dosing schedule or has incomplete data, a decision will be made on a case-by-case basis as to whether that subject should be included in the PK and PD analyses; however, data for all subjects will be presented in the data listings.

7.3 Disposition of Subjects

Disposition of all screened failure subjects will be summarized according to the primary reason for screen failure. Additionally, disposition information for screen failures will be listed.

Disposition of all randomized subjects will be summarized by pooled placebo, each TAK-418 dose level, TAK-418 overall and overall. The categories will include:

- Subjects who were randomized but not treated, if applicable.
- Subjects who completed the study drug.
- Subjects who prematurely discontinued the study drug.
- Subjects who completed all study visits.

• Subjects who prematurely discontinued study visits.

Primary reasons for discontinuing study drug and/or visits, as recorded on the eCRF, will be summarized.

Disposition information for randomized subjects will be listed. The status of blind for randomized subjects will also be listed. A listing of inclusion/exclusion criteria not met will be provided for randomized subjects who did not meet at least one inclusion criterion.

Significant protocol deviations captured on the eCRF will be listed and summarized.

7.4 Demographic and Other Baseline Characteristics

Demographic and baseline characteristics will be summarized for subjects in the Safety Set. Summaries will be presented by pooled placebo, each TAK-418 dose level, TAK-418 overall, and overall total. Summary statistics (number of subjects, mean, SD, median, minimum, and maximum) will be presented for continuous variables (eg, age, weight, and BMI), and the number and percentage of subjects within each category will be presented for categorical variables (eg, sex, ethnicity, and race). Individual subject demographic and baseline characteristic data will be provided in the data listings.

Demographic variables of screen failure subjects and reasons for screen failures will be summarized overall for subjects who are screened but not enrolled in the study. Individual demographic characteristics, date of informed consent, any available safety data and reason for screen failures will also be presented in the data listing.

There will be no inferential analysis of demographic and baseline characteristics.

7.5 Medical History and Concurrent Medical Conditions

Medical history is defined as significant conditions or diseases that resolved at or prior to the time of informed consent. Concurrent medical conditions are defined as significant conditions or diseases that are present or ongoing at signing of informed consent.

Medical history and concurrent medical conditions will be coded using the Medical Dictionary for Drug Regulatory Activities (MedDRA, version 19 or higher) coding system.

Medical history and concurrent medical conditions will be listed by site and subject number. The listing will contain subject identifier, treatment, system organ class (SOC), preferred term (PT), whether there was any medical history or concurrent condition, and, if yes, a detail of the medical history or concurrent condition.

There will be no inferential analysis of medical history and concurrent medical conditions.

7.6 Medication History and Concomitant Medications

Medication history information includes any medication relevant to eligibility criteria stopped at or within 28 days prior to signing of informed consent. Concomitant medications are recorded on the eCRF and include any medications, other than study drug, taken at any time from signing of informed consent through the end of the study.

All medication history and concomitant medications will be listed by site and subject number. The listings will contain subject identifier, treatment, World Health Organization Drug Dictionary (WHODrug) preferred medication name, dose, unit, frequency, route, start date, stop date, whether the medication was ongoing, and reason for use. No inferential statistics will be presented.

Medication history and concomitant medications will be coded using the WHODrug Version 01 March 2016 or higher.

7.7 Study Drug Exposure and Compliance

Each subject will be given a single dose as per the study design. Since all doses of study medication will be administered during confinement, study drug compliance will not be summarized. Dosing administration as well as study drug concentration data will be provided by subject and visit in the listings. Meal time and meal consumption will be listed as collected on the eCRF.

There will be no inferential analysis of study drug exposure.

7.8 Efficacy Analysis

Not applicable.

7.9 Pharmacokinetic/ Pharmacodynamic Analysis

7.9.1 Pharmacokinetic Analysis

All PK summaries and analyses will be based on the PK Set. PK parameters of TAK-418 will be derived using noncompartmental analysis methods and will be determined from the concentration-time data for all evaluable subjects. Actual sampling times, rather than scheduled sampling times, will be used in all PK computations involving sampling times for plasma PK parameters. Nominal time intervals will be used for computations of urine PK parameters.

PK blood and urine samples for TAK-418F concentrations will be collected as specified in the Schedule of Trial Procedures (See Appendix D). Plasma and urineTAK-418F concentrations will be measured by liquid chromatography with tandem mass spectrometry method.

Plasma concentrations of TAK-418F will be summarized by dose over each scheduled sampling time using descriptive statistics. The amount of TAK-418F excreted in urine will also be summarized by dose using descriptive statistics. Subjects randomized to placebo will not be included in these summarizes but will be listed. Individual plasma concentration and urine concentration versus time and PK parameters will be presented in a data listing.

The following pharmacokinetic parameters will be calculated for plasma concentration values of TAK-418F:

Symbol/Term	Definition
t _{max}	Time of first occurrence of C_{max} .
C_{max}	Maximum observed concentration.
AUC_{last}	Area under the concentration-time curve from time 0 to time of the last quantifiable concentration
AUC_{∞}	Area under the concentration-time curve from time 0 to infinity, calculated using the observed value of the last quantifiable concentration
CCI	

Descriptive statistics (N, arithmetic mean, SD, %CV, median, minimum, and maximum) will be used to summarize the plasma PK parameters for TAK-418 by dose. In addition, geometric mean will be computed for C_{max} and AUCs. Individual plasma PK parameters will be presented in a data listing.

The following pharmacokinetic parameters of TAK-418 will be derived from urine concentrations of TAK-418F:

Symbol/Term	Definition		
CCI			

Descriptive statistics (N, arithmetic mean, SD, median, minimum, and maximum) will be used to summarize the urine PK parameters for TAK-418. Individual urine PK parameters will be presented in a data listing.

Specific or additional PK parameters may be added as appropriate per the Clinical Pharmacology Analysis Plan (CPAP).

If sufficient data are available, the does proportionality for cohorts (fasted cohorts only) on Day 1 for key PK parameters (C_{max} and AUCs) will be assessed using the power model. The power model can be described by the following equation:

$$ln(PK\ Parameter) = \beta_o + \beta_1 ln(Dose) + \varepsilon$$

where β_o is the intercept and β_1 is the slope with random error ε . Dose proportionality will be declared if the 90% confidence interval (CI) for β_1 lies entirely within the critical region,

$$\left(1 + \frac{\ln(0.80)}{\ln(r)}, 1 + \frac{\ln(1.25)}{\ln(r)}\right)$$

where r is the ratio of the highest and the lowest dose in the study. [3]

For evaluation of potential food effect on TAK-418F PK, log-transformed C_{max} and AUC values for Cohort 3 will be compared between the treatments (Reference=fasting administration; Test=fed administration) using an analysis of variance (ANOVA) with fixed effect for treatment and a random effect for subject. The geometric mean for relative bioavailability and 90% CIs of geometric mean ratio for C_{max} , AUC_{last} , and AUC_{∞} will be calculated.

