#### **6.2** Dose Escalation

Dose escalation and subsequent dose levels will be based on a blinded review of available safety (including neurological assessment) and tolerability data from the previous dose levels and will only occur following agreement between the investigator and the sponsor. PK data will be used to guide dose selection after each cohort.

Following Cohort 1, subsequent dose levels may be higher, may be lower, or may remain the same as the preceding dose level. After Cohort 2, dose escalations will be limited to an escalated dose that is predicted to give no greater than a 3-fold increase in either  $C_{max}$  or AUC of the immediate prior dose level. Dosing will continue as long as the mean AUC of the highest dose level is predicted not to exceed the mean area under the serum concentration-time curve from time 0 to 24 hours (AUC24) at the no effect level for  $^{CCI}$ findings in male monkeys (the more sensitive species) from the 13-week toxicology study (CCI ) or the mean  $C_{max}$  of the highest dose is predicted not to exceed one-tenth of the mean  $C_{max}$  of the NOAEL from the 4 weeks toxicology study in monkeys (CCI ). If needed, a higher dose than the planned dose of 180 mg but less than 300 mg will be evaluated providing that the predicted exposure of this dose does not exceed the exposure levels mentioned above. If the majority of plasma concentrations of TAK-418F are below the limit of detection, the dose will be escalated to the next planned dose level provided safety and tolerability at the preceding dose level are considered acceptable.

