### 11.1.3 PK Analysis

Plasma concentrations of TAK-418F will be summarized by dose over each scheduled sampling time using descriptive statistics.

The amount of TAK-418F excreted in urine will be summarized by dose using descriptive statistics

Individual plasma and urine concentration versus time and PK parameter data will be presented in a data listing.

Plasma and urine PK parameters of TAK-418F will be summarized by dose using descriptive statistics.

If sufficient data are available, dose proportionality of TAK-418F plasma exposures ( $C_{max}$  and AUC) will be assessed statistically using a power model. For evaluation of potential food effect on TAK-418F PK, log-transformed  $C_{max}$  and AUC values will be compared between the treatments (Reference=fasting administration; Test=fed administration) using an analysis of variance (ANOVA) with fixed effect for treatment and a random effect for subject. The geometric mean relative bioavailability and 90% CIs for  $C_{max}$ , AUClast, and AUC $_{\infty}$  will be calculated based upon the adjusted means (LS means) from the ANOVA.

A more detailed analysis will be presented in the SAP. Additional analyses will be included, if appropriate.

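### Does the dose-proportionality rule need stated conclusions for a confidence interval that crosses a limit or lies wholly outside the region?

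*SAP*

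**What the plan says.** Protocol 11.1.3 says that dose proportionality of Cmax and AUC will be assessed with a power model if the data suffice, and leaves the detail to the SAP: "A more detailed analysis will be presented in the SAP".

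SAP 7.9.1 regresses the log parameter on log dose in the fasted cohorts. "Dose proportionality will be declared if the 90% confidence interval (CI) for" the slope lies entirely between 1 + ln(0.80)/ln(r) and 1 + ln(1.25)/ln(r), "where r is the ratio of the highest and the lowest dose in the study". A published method is cited. No other outcome is named. For the food effect, the next paragraph reads "The geometric mean for relative bioavailability and 90% CIs of geometric mean ratio for" Cmax, AUClast and AUC∞ will be calculated.

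Three other places bear on the point:

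- SAP 7.1 (General Principles) sets the number of decimal places at which confidence intervals for parameter estimates are presented.
- SAP 7.2 lets the analysed subjects differ by parameter: "All subjects with valid PK parameter estimates will be included in the summaries and analyses for that parameter".
- Protocol 6.2 foresees a dose level at which concentrations are mostly undetectable: "If the majority of plasma concentrations of TAK-418F are below the limit of detection", escalation continues to the next planned dose if safety and tolerability allow.

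**The concern.** A rule with one named outcome puts two different findings under one heading. An interval of 0.80 to 1.20 is centred on proportionality but too wide to show it. An interval of 1.30 to 1.50 shows clear non-proportionality. Neither meets the condition, so neither is declared. A report that gave only that result could be misread as evidence of non-proportional exposure. The paragraph also has no sentence saying that the slope and its interval will be tabulated.

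The second worry is r. If 5 mg gave no valid AUC∞, for example, the regression would start at 15 mg while r still counted 5 mg. The region would then be too narrow for the range analysed.

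At stake is the wording of a secondary PK conclusion. Dose escalation under Protocol 6.2 rests on predicted exposure and reviewed data, not on this test.

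**Working it through.** The plan states no power or numeric region for this analysis, so there is no figure to reproduce. The check applies the SAP's own formula.

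**Inputs.** Six active subjects per dose (SAP 6.0). Doses of 5, 15, 30, 40, 60 mg (SAP Table 4.a) or 5, 15, 45, 90, 180 mg (Protocol Table 6.a). A 90% interval for the slope. The between-subject CV is an assumption, taken from 15% to 40%.

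**Region.** The half-width is ln(1.25)/ln(r).

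- 5–60 mg: r = 12, 0.2231/2.4849 = 0.090, region 0.910 to 1.090.
- 5–180 mg: r = 36, 0.2231/3.5835 = 0.062, region 0.938 to 1.062.

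**Precision.** The log-scale SD is s = √ln(1+CV²) and the slope SE is s/√Sxx. Sxx is 22.81 for 5–60 mg and 48.85 for 5–180 mg, with 28 degrees of freedom and t = 1.701. At CV 30%, s = 0.2936:

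- 5–60 mg: interval half-width 1.701 × 0.2936/√22.81 = 0.105, against 0.090.
- 5–180 mg: 1.701 × 0.2936/√48.85 = 0.071, against 0.062.

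Above a CV of about 26%, even an estimate of exactly 1 would typically miss.

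**Outcomes** (1,000,000 simulated slopes per scenario; inside / crossing a limit / wholly outside, %):

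| True slope | CV | 5–60 mg | 5–180 mg |
|---|---|---|---|
| 1.0 | 15% | 75 / 25 / 0 | 77 / 23 / 0 |
| 1.0 | 20% | 36 / 64 / 0.02 | 38 / 62 / 0.02 |
| 1.0 | 30% | 1.4 / 98.4 / 0.2 | 1.7 / 98.1 / 0.2 |
| 1.1 | 30% | 0.4 / 92.7 / 6.9 | 0.1 / 77.8 / 22.1 |
| 1.2 | 20% | 0 / 17 / 83 | 0 / 0.1 / 99.9 |
| 1.2 | 30% | 0 / 46 / 54 | 0 / 6 / 94 |
| 1.2 | 40% | 0 / 62 / 38 | 0 / 21 / 79 |

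At CV 30% the condition therefore fails in 98.6% or 98.3% of trials at slope 1 and in essentially all at slope 1.2. The bare result barely distinguishes the two, but the interval often does: it is wholly outside in 0.2% of trials at slope 1, against 54% or 94% at slope 1.2.

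**What the text makes available.** The rule cannot be applied without computing the slope's 90% interval and the region. The food-effect sentence likewise promises only calculation, so the two paragraphs stand on the same footing. SAP 7.1 presupposes that estimates and their intervals are presented, although as a formatting rule it is not a commitment to a slope table. The information that separates the cases is thus already produced.

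**The r question.** If every fasted dose contributes at least one valid estimate, the two definitions of r agree. Suppose 5 mg contributes none (22 degrees of freedom; Sxx = 6.14 for 15–60 mg, 20.21 for 15–180 mg). The chance of declaring at true slope 1 is then:

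| CV | 15–60 mg: r = 4 (regression) vs 12 (study) | 15–180 mg: r = 12 vs 36 |
|---|---|---|
| 15% | 65% vs 2% | 67% vs 17% |
| 20% | 25% vs 0.06% | 27% vs 1.3% |
| 30% | 0.8% vs 0% | 0.9% vs 0% |

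Study-wide r makes declaration harder. With r = 12 over a remaining 4-fold range, the exposure limit becomes exp(0.0898 × ln 4) = 1.13 instead of 1.25. It cannot produce a false declaration.

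**The case for a change.** The strongest case for a change is that it costs only wording. The SAP is where the protocol places the detail, and the visible reference to the separate clinical pharmacology plan concerns only additional PK parameters. Three stated outcomes would guard against reading a miss as non-proportionality. Once a conclusion of non-proportionality existed, study-wide r would no longer be harmless. At a true slope exactly on the correct limit for a regression without 5 mg, the chance of that conclusion would rise from 5% to 31% (15–60 mg) or 20% (15–180 mg) at CV 15%, and to 14% or 11% at CV 30%.

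The arithmetic stands, and so does the observation that only one outcome is named. The inference to a defect does not. The SAP draws no conclusion of non-proportionality from this test, so the inflated rates belong to a label it does not contain. The r scenario needs an end dose with no valid estimate at all; mostly undetectable concentrations do not by themselves mean that, and the analysis is already conditional on sufficient data. Taking r from the regression also has a cost: a single quantifiable subject at an end dose could set the region, which could then differ between parameters.

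Separately, SAP Table 4.a stops at 60 mg while the SAP text reads "Doses planned to be administered range from 5 to 180 mg", in line with Protocol Table 6.a. Those passages must be reconciled. The mismatch does not alter this rule, because r is computed from the doses actually given.

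**Conclusion.** No change to the plan is needed. The criterion is a sound inclusion rule: it says when proportionality may be claimed and makes no claim otherwise, so following it as written leads to no wrong conclusion. Extra labels would change no estimate, no sample and no probability of declaring. At slope 1 and CV 30%, the added label would be 'inconclusive' in about 98% of trials. A modest departure (slope 1.1, CV 30%) would also mostly stay there, with the interval wholly outside in only 7% (5–60 mg) or 22% (5–180 mg).

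A competent analyst will show the slope, its 90% interval and the region, and will describe a crossing interval as inconclusive. If an end dose drops out of a regression, the same analyst will limit the statement to the range analysed. Writing this down would be an optional clarification.

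The percentages rest on an assumed CV, six evaluable subjects per dose and normal errors on the log scale. The judgement that no change is needed does not depend on the CV chosen. It rests on the form of the rule and on the standing of the analysis: conditional, secondary and, under SAP 6.0, without a power calculation.
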